## 3. Objectives and hypotheses

---

### 3.1 Primary objectives

#### 3.1.1 Primary security objective

To evaluate the safety of ophthalmic application of Nanodrop® by quantifying the incidence of unexpected Adverse Events (AEs).

#### 3.1.2 Primary efficacy objective

To demonstrate the non-inferiority of Nanodrop® compared to Systane® Balance in the treatment efficacy of patients with dry eye, using the OSDI (Ocular Surface Disease Index) test score.

### 3.2 Secondary objectives

#### 3.2.1 Secondary security objective

To compare the safety of ophthalmic application of Nanodrop® versus Systane® Balance by quantifying the incidence of expected adverse events.

#### 3.2.2 Secondary efficacy objectives

To compare the efficacy of ophthalmic application of Nanodrop® versus Systane® Balance through changes in BCVA.

To compare the efficacy of ophthalmic application of Nanodrop® versus Systane® Balance by changes in conjunctival staining with lissamine green.

To compare the efficacy of ophthalmic application of Nanodrop® versus Systane® Balance using changes in corneal fluorescein staining.

To compare the efficacy of ophthalmic application of Nanodrop® versus Systane® Balance by means of changes in TRPL.

### 3.3 Exploratory objectives

Compare the average daily applications of Nanodrop® versus Systane® Balance.

### 3.4 Hypothesis

#### 3.4.1 Security hypothesis

$H_0$  = Nanodrop® is safe in its ophthalmic application, presenting an incidence of unexpected AEs, related to the PI less than 20% of the population of the Nanodrop® safety group

$H_1$  = Nanodrop® is not safe for ophthalmic application, as it presents an incidence of unexpected AEs related to the PI greater than 20% of the population in the Nanodrop® safety group.

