## 7.4.4 Definition of variables, methods and scales to be used for measurement

Variable	Guy	Unit (symbol)	Measurement method	Normal value	Evaluation time	Statistical test
Primary outcome						
OSDI	Discreet	Points (-)	Questionnaire	< 13	VB and VF	Mann-Whitney U
Unexpected EAs related to PI	Discreet	Number of cases (n)	Counting	0	VB, V1 and VF	Mann-Whitney U
Unexpected AEs related to the PI (bis)	Nominal categorical	Present/absent (-)	Observation	Absent	VB, V1 and VF	$\chi^2$ or Fisher's exact test
Of secondary outcome						
MAVC	Discreet	Fraction (-)	Snellen chart	1	VB, V1 and VF	Mann-Whitney U
TRPL with fluorescein	Continue	Seconds (s)	Direct observation with slit lamp and blue filter	>10s	VB, V1 and VF	Mann-Whitney U
Corneal staining with fluorescein	Ordinal	Degrees (-)	Direct observation with a slit lamp on the Oxford scale	0	VB, V1 and VF	$\chi^2$ or Fisher's exact test
Conjunctival staining with lissamine green	Ordinal	Degrees (-)	Direct observation with slit lamp and cobalt blue filter, Oxford scale graduation	0	VB, V1 and VF	$\chi^2$ or Fisher's exact test
EA	Discreet	Number of cases (n)	Counting	0	VB, V1 and VF	Mann-Whitney U
EA (repeat)	Nominal categorical	Present/absent (-)	Observation	Absent	VB, V1 and VF	$\chi^2$ or Fisher's exact
Exploratory						
Number of applications made daily	Discreet	Number of applications (n)	Count by Subject's Diary	>4	V1 and VF	Mann-Whitney U

**Table 2**Operational definition of variables

The variables, method, and scales for their measurement are described in detail below. They are listed in order according to **Table 2**

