### 10.1.2 Data interpretation

The Kolmogorov-Smirnov and Shapiro-Wilk tests will be performed, as applicable, to determine whether the distribution is normal in the results obtained in each study group.

The results of continuous quantitative variables will be presented in measures of central tendency: mean, standard deviation and ranges.

The statistical analysis of continuous quantitative variables to find significant differences (  $p<0.05$  ) will be as follows:

- Intra-group analysis: will be determined using the Wilcoxon rank test for quantitative variables.
- Between-group analysis: Differences between groups will be analyzed using the Student t-test or the Mann-Whitney U statistic if applicable ( it will be used to test whether a group of data comes from the same population).

The level of difference considered significant will be an alpha ( $\alpha$ ) of 0.05 or less. A 95% CI will be considered for noninferiority criteria.

The results of the nominal and ordinal qualitative variables will be presented in frequencies, proportions and percentages.

Statistical analysis to identify significant differences in qualitative variables will be performed by creating 2x2 contingency tables and will be carried out as follows:

- Intra-group difference: McNemar's test. This test is applied to 2x2 contingency tables with a dichotomous trait, with matched pairs of subjects, to determine whether the marginal frequencies of the row and column are equal (marginal homogeneity).

- Difference between groups: Pearson's Chi-square test (  $X^2$  ) or Fisher's exact test for expected values less than 5.

The level of difference to consider significance will be an alpha ( $\alpha$ ) of 0.05 or less.

For adverse event reporting, all eyes of participants randomized to an intervention group after the baseline visit will be considered. Results will be expressed as the number of subjects.

The final results report will be displayed in tables or graphs, as appropriate.

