#### 10.1.3 Procedure for handling missing data

Safety: The safety assessment will include in the analysis all subjects (both eyes) who have been exposed at least once to any of the interventions. Subjects enrolled in the efficacy phase will be included in the safety analysis for this phase, regardless of the visit at which they were eliminated from the study (ITT; intention-to-treat population).

Efficacy: Subjects who meet a minimum adherence of 70% will be included in the statistical analysis to meet the study objective, based on the weight of the PI. In cases where the container is not returned or has not been physically intact, adherence will be measured using the subject's diary.

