#### 10.1.5 Subjects included in the analysis

A preliminary safety analysis will be performed upon completion of follow-up of subject 12 in the Nanodrop® group (Phase I).

If fewer than 20% of unexpected drug-related AEs occur in the Nanodrop® group, enrollment for the efficacy analysis (Phase II) will be completed. Otherwise, the study will be terminated.

For phase II of the study, those subjects who meet a minimum adherence of 70% will be included in the statistical analysis to meet the study objective (PP; per-protocol population).

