2.0 Objectives of the Study

Security (Phase I):

To evaluate the safety of ophthalmic application of Nanodrop® by quantifying the incidence of unexpected Adverse Events (AEs) related to the investigational product (IP).

Efficacy (Phase II):

To demonstrate the non-inferiority of Nanodrop® compared to Systane® Balance in the treatment efficacy of patients with dry eye, using the OSDI (Ocular Surface Disease Index) test score.

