4.0 Sample Size

An estimated 63 subjects (both eyes) per treatment arm are planned (Phase I: 12 subjects / Phase II: 114 subjects).

[figure not shown]

Figure 1. Suggested workflow. ITT: Intention-to-treat population; PP: Per-protocol population.

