The statistical analysis of continuous **quantitative variables** to find significant differences (p) will be as follows:

- Intra-group analysis: will be determined using the Wilcoxon rank test, for quantitative variables (Woolson, 2008).
- Between-group analysis: differences between groups will be analyzed using the Student t-test or the Mann-Whitney U statistic if applicable (it will be used to test whether a group of data comes from the same population).

The level of difference to consider significance will be an alpha (α) of 0.05 or less. It will be considered a 95% CI for non-inferiority criteria (Schumi & Wittes, 2011; Easty et al., 2006).

The result of the nominal and ordinal qualitative variables will be presented in frequencies, proportions and percentages, see table 2.

Statistical analysis to identify significant differences in **qualitative variables** will be performed by creating 2x2 contingency tables and will be carried out as follows:

- Intra-group difference: McNemar's test (Klingenberg & Agresti, 2006). This test is applied to 2x2 contingency tables with a dichotomous trait, with matched subject pairs, to determine whether the marginal frequencies of the row and column are equal (marginal homogeneity).
- Difference between groups: Chi-square test (χ^2) Pearson's or Fisher's exact test in values expected under 5.

The level of difference to consider significance will be an alpha (α) of 0.05 or less.

For the reporting of adverse events, all eyes of participants who were randomized to an intervention group after the baseline visit will be considered.

The final results report will be displayed in tables or graphs, as appropriate.

Subjects who meet a minimum adherence of 70% will be included in the statistical analysis to meet the study objective, based on the weight of the PI. In cases where the container is not returned or has not been physically intact, adherence will be measured using the subject's diary.

The investigational drug will be considered safe and effective when there are no clinical and statistical differences in all primary outcome variables, with respect to its comparator.
(Systaine® Balance).

Table 3. Triangulation of concepts

Variable Type	Variable	A1	B1	B2	C1	C2	D1	E1	E2	E3
Background										
A1	Demographics						DT			
Basal										
B1	Medical record				DT					
B2	Comprehensive ophthalmological evaluation				DT		TB	TB		TB
Security										
C1	Unexpected/related AEs				TB		TB		TB	TB
C2	EAs				TB		TB		TB	TB

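### The primary safety hypothesis is set against 20%, but no planned test or interval refers to 20%, and SAP 7.0 concludes safety from the absence of a difference between arms

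*Protocol*

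**What the plan says.** - **Hypothesis.** Protocol 3.4.1 concerns Nanodrop alone. Under the null the product is safe, "presenting an incidence of unexpected AEs, related to the PI less than 20% of the population of the Nanodrop® safety group"; under the alternative the incidence is above 20%. The primary safety objective (Protocol 3.1.1) names no comparator.
- **Use of 20%.** Protocol 10.1.5 applies it to the preliminary analysis after subject 12 of the Nanodrop arm: "If fewer than 20% of unexpected drug-related AEs occur in the Nanodrop® group, enrollment for the efficacy analysis (Phase II) will be completed"; a proportion of 20% or more ends the study. Protocol 1.1 and 4.1 and SAP 3.0 and 7.0 repeat the rule. None attaches a test or an interval to it.
- **Tests.** Protocol Table 2 (7.4.4) gives the event count a Mann-Whitney test and the present/absent version a chi-square or Fisher test. Protocol 10.1.2 specifies Pearson chi-square between groups, "or Fisher's exact test for expected values less than 5". It and SAP 7.0 also list intra-group Wilcoxon and McNemar tests. The 95% confidence interval is mentioned only for non-inferiority.
- **Final rule.** SAP 7.0: "The investigational drug will be considered safe and effective when there are no clinical and statistical differences in all primary outcome variables", relative to Systane Balance.
- **Who is counted.** The safety group is not defined. SAP 2.0 assigns the safety objective to Phase I. SAP 4.0 gives "Phase I: 12 subjects / Phase II: 114 subjects", whereas Protocol 10.2.1 puts 24 subjects (12 per group) in the safety phase and 102 in the final phase. Protocol 10.1.3 says: "The safety assessment will include in the analysis all subjects (both eyes) who have been exposed at least once to any of the interventions".

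**The concern.** The hypothesis asks whether incidence on Nanodrop is below a fixed limit. The final rule asks whether the two arms differ. These are different questions, and a non-significant comparison does not answer the first. If both products cause unexpected related events at a similar high rate, the SAP rule is satisfied while the protocol's own limit is exceeded. What is at stake is the wording of the trial's conclusion on one of its two primary outcomes: the report could call Nanodrop safe under a prespecified rule that does not involve the 20% limit.

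**Working it through.** The documents give no sample size, significance level, sidedness or power for the 20% hypothesis, so there is no planned figure to reproduce. They also give no expected event rate for either arm; all true rates below are assumptions, shown as a range.

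**Inputs.** 12 Nanodrop subjects at the gate (Protocol 10.1.5); 63 per arm at the end (Protocol 10.2.1); limit 20% (Protocol 3.4.1); counting unit the subject with an event (SAP Table 2); two-sided 0.05 for the between-arm test.

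**1. The gate.** Since 2/12 = 16.7% and 3/12 = 25%, an observed proportion below 20% means at most 2 of 12. The chance of passing is the sum over k = 0 to 2 of C(12,k) p^k (1−p)^(12−k):

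- p = 20%: 0.069 + 0.206 + 0.283 = 0.558
- p = 25%: 0.391
- p = 30%: 0.014 + 0.071 + 0.168 = 0.253

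The best possible result, 0/12, has an exact one-sided 95% upper limit of 1 − 0.05^(1/12) = 22.1%. For 2/12 it is 43.8%. No result at the gate can show an incidence below 20%.

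**2. The no-difference rule at equal high rates.** Take 19/63 in each arm. Incidence is 30.2% in both and p = 1.0. The exact one-sided 95% lower limit for 19/63 (the 5% quantile of a Beta(19, 45) distribution) is 20.7%, so the data place incidence above 20% at that level while the rule finds no difference. The lower end of a two-sided 95% interval would be 19.2%.

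**3. Gate and final test together.** Exact enumeration: at most 2 events in the first 12 Nanodrop subjects, 51 more added, compared with a binomial count in 63 comparator subjects by uncorrected Pearson chi-square, or by Fisher's test when an expected value is below 5. A pass means p > 0.05.

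| Assumed true rate, Nanodrop v comparator | Passes gate and final test |
|---|---|
| 30% v 30% | 24% |
| 25% v 25% | 37% |
| 30% v 10% | 8% |
| 30% v 5% | 1% |

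These figures cover the safety component only. The SAP rule spans all primary outcomes, so OSDI must also show no difference. They use the present/absent version, not the Mann-Whitney test on counts.

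**4. How often the example in step 2 is reached.** Passing the gate and then ending with at least 19/63 has probability 0.7%, 3.6%, 7.9% and 9.3% at true rates of 20%, 25%, 30% and 35%.

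**5. What a claim of incidence below 20% would need.** With 63 exposed, the exact one-sided 95% upper limit is 19.9% for 7/63 and 21.7% for 8/63, so at most 7 events. The upper end of a two-sided 95% interval is 19.6% for 6/63 and 21.6% for 7/63, so at most 6.

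**The case against.** The strongest reply is that 20% was only ever a Phase I screen, and that the screen is fully specified. SAP 2.0 ties the safety objective to Phase I, 3.4.1 speaks of a safety group, the objective is to quantify incidence, and Protocol 10.1.3 can be read as analysing safety by phase. That reading is at least as natural as a final test, and it stands. A reader might infer that the protocol promised a confirmatory test against 20% and then omitted it; the documents do not establish that. But on the screen reading 3.4.1 is still a formal hypothesis with no test, and SAP 7.0 still draws its conclusion from the between-arm result.

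Other replies stand in part:

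- The final percentage will be reported. That is so, but a reported figure does not override a written decision rule.
- The gate and a comparator with a low rate give real protection, as step 3 shows, and the example in step 2 is uncommon.
- A clinical difference might be found even with equal counts, for instance in intensity, which SAP Table 2 grades. The term is undefined, so this cannot be relied on; on incidence itself, equal counts do not differ.

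Three stronger inferences should be resisted. With safety as the null, one might say that sparse data favour a safe conclusion; that holds only if the null is formally tested, and no such test is planned. One might say that the rule would penalise Nanodrop for having fewer events (0/63 v 6/63 gives Fisher p = 0.028); that requires counting a favourable difference against it, which is a strained reading. And it would be wrong to say that only between-arm tests are planned: intra-group tests are listed too, though they do not address 20% either.

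**Conclusion.** The point holds as a mismatch between a stated hypothesis and a stated conclusion rule. The protocol's 20% limit has no inferential use; the 12-subject look can screen but cannot show that incidence is below it; and the SAP's only final route to calling the product safe does not track it. The size depends on the comparator's true rate, which is unknown: at a true 30% on Nanodrop, the gate and final test together are passed about 24% of the time if the comparator is also at 30%, 8% if it is at 10% and 1% if it is at 5%. These figures assume 63 exposed per arm, subjects as the counting unit, and a statistical difference as the criterion. If a difference must be both clinical and statistical to fail the rule, pass rates could only be higher. The trial can run as designed. What should change before analysis is the rule that turns a non-significant comparison into a statement of safety.

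**What to change.** Leave the 12-subject rule as it is. Then:

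1. State in Protocol 3.4.1 that 20% is a Phase I screen.
2. Define the safety group and reconcile the 12 subjects of SAP 4.0 with the 24 of Protocol 10.2.1.
3. At the end, report Nanodrop incidence (subjects with at least one unexpected related event, over all exposed) with an exact confidence interval.
4. Report the between-arm comparison of these events descriptively, and remove safety from the no-difference rule in SAP 7.0.

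This costs wording and one interval, with no added subjects or visits.

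Only if the sponsor wants to claim an incidence below 20%: restate the null as incidence of 20% or more, and require the exact upper limit to be below 20%. With 63 exposed that means at most 7 events (one-sided 95%) or at most 6 (two-sided 95%). The plan sets no level, so the sponsor must choose one. The cost is a harder claim: at an assumed true 10% it is met 71% and 56% of the time respectively, before allowing for the gate. The threshold should be computed from the actual number exposed, because replaced subjects stay in the safety analysis (Protocol 5.3.1). With 62 exposed the one-sided limit is 6 events, and the chance at a true 10% falls to 57%.

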### 3.4.2 Efficacy hypothesis

$H_0$  = Nanodrop® is inferior to Systane® Balance by more than 5 points on the OSDI test score

$$H_0: \mu_A - \mu_B > \delta$$

$H_1$  = Nanodrop® is inferior to Systane® Balance by 5 points or less on the OSDI test score

$$H_1: \mu_A - \mu_B \leq \delta$$

## 4. Study design

---

### 4.1 Design Overview

Phase I-II, comparative, non-inferiority, active-controlled, parallel-group, double-blind, randomized clinical trial. Safety analysis is performed upon completion of the first 12 subjects in the Nanodrop® group. If fewer than 20% of unexpected AEs related to the investigational product occur, recruitment continues until the sample size for efficacy analysis is complete. (See pp. 14)

### 4.2 Justification of the study design

Propylene glycol, a component of Nanodrop®, is a compound classified by the FDA as GRAS for use in food, cosmetics, and drug products. The propylene glycol concentration falls within the specifications of the FDA monograph for ophthalmic lubricants considered safe.

Because of this, the design of a separate Phase I study is not considered necessary; the advantages of the proposed design include having data on the efficacy variables from all subjects included in the study for the efficacy analysis. The safety phase will allow for the identification of unforeseen risks related to the study's formulation or procedures without interfering with the efficacy analyses.

### 4.3 Expected duration

The total duration of the study, from the first patient visit to the final report, is estimated to be 11 months.

The planned recruitment period is 9 months. Considering the proposed sample size of 126 subjects, the average recruitment rate throughout the study should be no less than 0.5 subjects per day.

The approximate duration of each subject in the study is 35 days.

## 5. Study population

---

### 5.1 Eligibility criteria

#### 5.1.1 Inclusion criteria

- Have the ability to voluntarily grant signed informed consent.
- Be able and willing to comply with scheduled visits, treatment plan, and other study procedures.
- Be willing to modify your lifestyle activities. See 5.3 **Lifestyle considerations**.
- Be of age.
- Women of childbearing potential must ensure continued use (started  $\geq$  30 days prior to signing the FCI) of a hormonal contraceptive method or IUD during the study period.
- Present diagnosis of dry eye, defined by:
  - OSDI  $\geq$  13 points
  - + 1 of the following:
    - Corneal staining with more than 5 sites
    - Conjunctival staining with more than 9 sites
    - Tear film break-up time  $<$  10 seconds

#### 5.1.2 Exclusion criteria

- For women: be pregnant, breastfeeding, or planning to become pregnant during the study period.
- Having participated in another clinical research study  $\leq$  30 days prior to the screening visit.
- Having previously participated in this study.
- Present a BCVA of 20/200 or worse in either eye.
- Present an additional ophthalmological diagnosis of:
  - Allergic, viral or bacterial conjunctivitis.
  - Anterior blepharitis.
  - Demodex.
  - Parasitic eye infections.
  - Unresolved ocular trauma.
  - Healing diseases of the ocular surface.
  - Corneal or conjunctival ulcers.
  - Filamentous keratitis.
  - Neurotrophic keratitis.
  - Bullous keratopathy.
  - Neoplastic diseases of the ocular surface or annexes.
  - Diseases with fibrovascular proliferations on the conjunctival and/or corneal surface.
  - Diseases of the retina and/or posterior segment that require treatment or threaten the visual prognosis.
  - Glaucoma.
- Have dry eye management that requires implementation of Stage 2 treatments in the DEWS II Staged Treatment and Management for Dry Eye Disease recommendations. See **Table 2**.

- Have a history of drug addiction or dependence, currently or within the last two years prior to signing the FCI.
- Have a history of ocular surgical procedures within the last 3 months prior to signing the FCI.
- Wear soft or hard contact lenses. You may be admitted if you can discontinue use of contact lenses during the study. You must not wear contact lenses for 15 days prior to enrollment.
- Having another medical condition, acute or chronic, that, in the opinion of the investigator, could increase the risk associated with participation in the study or the administration of the investigational product, or that could interfere with the interpretation of the study results.
- Have a known hypersensitivity to the components of the investigational products.
- Be or have an immediate family member (e.g., spouse, parent/legal guardian, sibling, or child) who is an employee of the research site or the sponsor and who is directly involved in this study.

## 5.2 Criteria for eliminating and replacing subjects

### 5.2.1 Elimination criteria

- Withdrawal of the FCI letter.
- Presentation of a serious adverse event, whether or not related to the investigational product, which, in the opinion of the PI and/or the sponsor, could affect the patient's ability to safely continue study procedures.
- Non-tolerability or hypersensitivity to any of the compounds used during the tests (fluorescein, lissamine green, tetracaine).
- Non-tolerability or hypersensitivity to any of the investigational drugs.

